clinical practices on a patient-by-patient basis, and because their obesity-prevention practices will likely be influenced by their exposure to FNPA (i.e., “contamination” concerns). The cluster design isn’t without disadvantages. This design has the potential for imbalance of the number of subjects across PCP resulting in possible imbalance at the intervention level. Also, analyses are complicated with a small number of clusters (<20). To overcome these disadvantages, we have compensated for potential imbalance in the sample size calculations. Lastly, our chosen method of analysis appropriately handles imbalance and combined with a large number of clusters, a total of 60, we do not anticipate concerns in the implementation and analysis.

A stratified design will be used to reduce the imbalance of covariate distributions between intervention arms. Prior to randomization, PCPs will be stratified based on the type of clinic in which they practice (Pediatrics versus Community Medicine) and case load (number of annual WCV conducted among the target population; low volume (< 52 WCV/year) or high volume > 52 WCV/year), as heavy patient volume can disrupt workflow and may affect intervention delivery.^{99,100} Since stratification can only address a limited number of potential confounders, initial analyses will examine other covariates known to influence clinical interventions and/or childhood obesity such as parent BMI, child baseline weight status, biological sex and race/ethnicity.

CORRECTION: Per discussion with the study team and PCORI in October 2022, it was observed that stratification details are an error. Per study documents, in August 2020 the study team observed that all but one pediatrician had a volume <52 WCVs in 2019, the past year, and Year-to-Date assessments; conversely, all Community Medicine providers had <52 WCVs. Therefore, 2 strata characterized: Pediatricians and Community Medicine. The Community Medicine providers were further stratified by those with <32 WCVs/year and those with ≥32 WCVs/year to align with clinic eligibility criteria: “Eligible clinics will have ≥1 PCPs with at least 32 qualifying well child visits annually for children aged 20 to 60 months, ≥50th BMI-for-age and -sex percentile.”

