During the start-up of the study we will develop a formal Data Management Plan to document how data will be collected, organized, stored, as well as a statistical analysis plan. Descriptive statistics will include evaluation of all data for underlying distribution and summary statistics, using means with standard deviations and medians with interquartile range for continuous variables, and frequency with percentages for categorical variables. The data will be summarized for all patients enrolled and will be stratified by randomization arm and study time point. We will assess the quality of data, evaluating outliers and patterns of missing data using graphs such as histograms and stem-and-leaf plots. Bi-variate analyses will be used to assess differences in patients (e.g., parent BMI, child biological sex, baseline BMI) between randomization arms. Since it is not recommended to perform inferential statistics to assess balance of baseline participant, family, community, and physician factors in a randomized study, we will use standardized differences.¹⁰³ Any standardized difference > 0.10 will be considered unbalanced and, thus, a potential confounding variable. We will also follow the CONSORT¹⁰⁴ extension to cluster randomized trials when reporting results.

As data is collected from participants as part of this research study, in an effort to facilitate additional analyses, the Geisinger study team plans to share a de-identified data set with PSU. This data set will be shared utilizing Geisinger IT-approved methodologies (Secure Transport, e-secure, etc.) to ensure that patient data is protected. These data will be stored at PSU in a secure network location that is only accessible to PSU study staff. These analyses will assist in exploring additional study research questions that may arise.

Aim 1. The primary outcome variable is change in BMIz at 12 months. BMIz is the most widely used obesity-related outcome per systematic review and thus was chosen for comparability with prior literature.^{11,105} The primary analysis will follow the “intention-to-treat” principal. That is, all participants enrolled will be analyzed according to their group assignment at the point of care (WCV) regardless of intervention received and compliance. Analyses will

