take into account the clustered nature of the study design. To test the Aim 1 hypothesis that participants will have a lower change in BMIz (and secondarily, changes in BMI, BMI50, BMIz extended) in Arms 2 and 3, as compared to Arm 1, mixed linear models^{106,107} with restricted maximum likelihood estimation will be fit. The models will include a random effect for PCPs and will be assumed to follow a Gaussian distribution. These analyses will adjust for the stratification factors used in the randomization scheme and any baseline variables found to vary across intervention arms as identified above. Contrast statements will be written as functions of the estimated regression coefficients to estimate the effect of the interventions compared to standard WCV using a two-sided alpha of 0.025 to account for multiple testing. Model assumptions will be examined (e.g., QQ plots to assess normally distributed residuals) and of the underlying Gaussian random effect distribution. Secondary analyses will estimate the effectiveness of the interventions on the percent of children overweight and obese (≥ 85 percentile of BMI and ≥ 95 percentile of BMI) at 12 months. A similar strategy will be employed using a generalized linear mixed model assuming a binomial distribution for the outcomes. These models will treat the binary outcomes as measured from the 12-month visit. Analysis of secondary outcomes in Aims 1b and 1c (involvement in preventive care, parent and home factors) will follow the same strategy as described above. Due to lagging enrollment, the study modified data collection for secondary outcome in specific aim 1b- involvement in preventive care- just after 50% enrollment was reached. The timing of this outcome measure was changed from pre-visit only to pre- or -post visit to allow for families to enroll and complete baseline data collection after a completed WCV. As there are complementary analysis methods for cluster randomized trials, we will also fit Bayesian random effect models¹⁰⁸⁻¹¹⁰ for continuous and binary outcomes. Each model will use an inverse gamma prior for the cluster random effect variance parameter.¹¹¹ We will note any differences in the effect estimates across methods.

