8. Demographics^{142,143} (Covariate) Factors that may be associated with provider adoption and effectiveness of intervention components, including specialty, training, experience, biological sex, race/ethnicity, age, self-reported height and weight status	BL	9	PCP-SQ
9. Attitudes, Norms, Perceived Behavioral Control and Intention about Obesity Prevention Intervention⁷⁹ (Mediator) Consistent with the Theory of Planned Behavior, PCPs' attitudes, perception of social norms, and perceived behavioral	BL FU 24 mo.	36	PCP-SQ

control regarding one's ability to modify FNPA risk factors will predict behavioral intentions and behavioral intentions will predict extent to which PCPs engage in the intervention			
10. Self-efficacy in Preventive Counseling for Obesity^{142,143} (Mediator) Training in and self-efficacy of providing obesity-related prevention and treatment (adapt for pediatrics)	BL FU 24 mo.	8	PCP-SQ
INDIVIDUAL-PARENT/CAREGIVER			
11. Perceived Involvement in Care¹⁴⁴ (Secondary Outcome) Scale measures parent perception of involvement in clinical encounter (adapt for WCV)	BL (pre or post WCV), FU	20	P-SQ
12. Food Resource Management^{23,92} (Secondary Outcome) Validated scales from the Cooking Matters® program assess participants' shopping behaviors and self-confidence in buying healthy foods and managing food resources	BL, 6 mo., FU	9	P-SQ
13. Demographics (Covariates) Biological sex, race/ethnicity, age, self-reported height and weight status, relationship to child, educational level, employment status	BL	11	P-TS
14. Attitudes, Norms, Perceived Behavioral Control and Intention about Obesity Prevention⁷⁸ (Mediator) Consistent with the Theory of Planned Behavior, parents' attitudes, perception of social norms, and perceived behavioral control regarding FNPA risk factors will predict behavioral intentions and behavioral intentions will predict extent to which parents engage in the intervention	BL	25	P-SQ

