Source: Secondary data sources are identified. A telephone survey (**TS**) will be used post- consent and prior to baseline well child visit. Electronic health record (**EHR**) will be referenced at baseline well child visit and follow-up. Other variables will be collected by study questionnaire (**SQ**) following the baseline well child visit.

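### The Aim 1 adjustment rule is not limited to variables measured before the index visit, so an early intervention effect on a questionnaire scale could be adjusted for as if it were confounding

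*Combined protocol and SAP*

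**What the plan says.** **The rule.** The Analytic Plan proposes to "assess balance of baseline participant, family, community, and physician factors in a randomized study, we will use standardized differences", and continues: "Any standardized difference > 0.10 will be considered unbalanced and, thus, a potential confounding variable". Under Aim 1, the mixed models for BMIz and the other BMI measures adjust for the stratification factors and for "any baseline variables found to vary across intervention arms as identified above". The wording is mandatory. It neither requires measurement before the index WCV nor excludes mediators. The examples in Research Design ("such as parent BMI, child baseline weight status, biological sex and race/ethnicity") are illustrative, not a closed list.

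**The timing.** The Source note under Appendix B, Table 4, says the telephone survey "will be used post- consent and prior to baseline well child visit". It then says: "Other variables will be collected by study questionnaire (SQ) following the baseline well child visit". The Timing note defines baseline only as at or near enrollment. The Aim 1 text says perceived involvement in care was collected only before the visit until just after 50% enrollment, and before or after it from then on, so that families could join after a completed WCV. Row 11 of Table 4 agrees. Study Procedures also allows recruitment after a completed WCV.

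**The variables exposed.** Parent study-questionnaire rows with a baseline time point include attitudes and intention (row 14, covering "perception of social norms, and perceived behavioral control regarding FNPA risk factors"), labelled Mediator and measured at baseline only; parenting practices (row 15, Mediator); perceived involvement (row 11, Secondary Outcome); and diet, activity, screen time and sleep (rows 16 to 19, Secondary Outcome, and named as mediators in Aim 2b).

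**The concern.** A variable measured before the intervention can differ between arms only by chance or through recruitment, and adjusting for it is harmless or helpful. A variable measured after the Arms 2 and 3 visit can differ because the visit worked. The rule does not distinguish the two cases, and it is more likely to select a scale the more the visit has moved it. Conditioning the primary contrast on such a scale takes out whatever part of the effect passes through it.

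The plan also treats one measurement in two ways. Under Aim 2, an arm difference in a hypothesised mediator is a step toward showing mediation. Under Aim 1, the same difference in the same baseline-only scale (row 14) is a potential confounder to be adjusted for.

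An answer given before the WCV is not always clear of the intervention either. For portal users the FNPA opens 14 days before the visit, with text reminders in Arms 2 and 3, so a questionnaire can precede the visit and still follow the FNPA.

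**Working it through.** **1. Reproduce the planned sample size.** Inputs from Sample Size and Power: d = 0.20, ICC = 0.005, coefficient of variation of cluster size 0.25, power 80%, 20 PCPs per arm. Alpha is 0.025, two-sided per Aim 1.

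- Without clustering: 2 × ((2.2414 + 0.8416)/0.20)² = 475.25 per arm.
- Design effect for m families per PCP: 1 + ((1 + 0.25²)m − 1) × 0.005. At m = 28 this is 1.144.
- 475.25 × 1.144 = 543.6, or 27.2 per PCP, rounded up to 28. That is 560 per arm, as stated.
- 560/(1 − 0.17) = 674.7, so 675 per arm, as stated.

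The sample size is not in error on this point.

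**2. How often the 0.10 rule flags a scale.** Assume the covariate has the same ICC as the outcome. At m = 675/20 = 33.75 the design effect is 1.174, and the SE of a standardized difference is √(2 × 1.174/675) = 0.059. For one pair of arms:

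| True shift in the measured scale (SD) | Probability flagged |
|---|---|
| 0 | 9% |
| 0.075 | 34% |
| 0.10 | 50% |
| 0.15 | 80% |
| 0.20 | about 95% |

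The 0.075 row is a 0.15 SD shift when only half the families answer after the visit. The shifts are assumptions; the documents give none.

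**3. What adjustment would remove, if a scale is flagged.** Write a for the shift in the scale and b for the SD of BMIz change per SD of the scale. The part removed is a × b, leaving 0.20 − ab. Power at 560 per arm is Φ(√(560 × (0.20 − ab)²/(2 × 1.144)) − 2.2414), with the outcome SD held at 1. With nothing removed it is 81%.

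| a | b | Effect left | Power |
|---|---|---|---|
| 0.075 | 0.05 | 0.196 | 80% |
| 0.075 | 0.10 | 0.193 | 78% |
| 0.15 | 0.05 | 0.193 | 78% |
| 0.15 | 0.10 | 0.185 | 74% |
| 0.15 | 0.27 | 0.16 | 60% |
| 0.15 | 0.33 | 0.15 | 54% |

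The slopes b are assumptions too. In the last two rows, allowing for the residual variance that such a covariate explains (residual SD √(1 − b²)) raises power to about 64% and 60%.

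**The case against.** **Timing.** A reader might infer from the Source note that every questionnaire baseline follows the intervention visit. The documents do not support that. Perceived involvement was pre-visit only for about the first half of enrollment. The reason given for the change suggests that post-visit baselines were a later accommodation. Families may be recruited up to six months ahead of the visit. A later-discontinued clinic pilot took parent attitudes before it. PCP questionnaires, which share the study-questionnaire label, are collected at or after training. This objection stands: timing is mixed, and the Source note conflicts with the Aim 1 text and row 11.

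**Role labels.** Table 4 marks rows as Covariate, Mediator, Moderator or Secondary Outcome. The parent and household Covariate rows come from the pre-visit telephone survey, and the child Covariate row comes from the EHR. The natural adjustment set may be just those rows. That is a sensible intention, but the Analytic Plan never refers to the labels and says any baseline variable. The labels supply the fix; they do not already contain it.

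**Mechanism.** Diet, activity, screen time and sleep are reported as usual or average levels near enrollment, and one visit has little time to move them. Arm 3 Food Care begins after the WCV and runs over 26 weeks, so its later effects are largely untouched. Both points stand. They narrow the exposure to attitudes, intention and perceived involvement, and to the visit-based component of Arms 2 and 3.

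**Size and direction.** Neither the shifts nor the slopes come from the documents. Confounding between mediator and outcome could push the bias either way. This also stands.

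**Conclusion.** The defect is in the rule as written. It can admit the trial's own mediators to the primary model, and does so more often the larger the early effect on them. Flagging rates of 80% at a 0.15 SD shift and 34% at 0.075 SD, against 9% under no effect, follow from the planned sample size, given a covariate ICC of 0.005.

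Two stronger conclusions are tempting and should not be drawn. One is that the intervention effect *would* be adjusted out. It *could* be, in part, if a scale was answered after the visit or the FNPA, was moved by it, crossed 0.10 and is associated with BMIz change. The other is that power falls to 54% or 60%. Those figures need a single scale with a slope of about 0.33 or 0.27 SD per SD and a full 0.15 SD shift. With slopes of 0.05 to 0.10, power stays between 74% and 80%. Attenuation toward no difference is the most plausible direction, not a certain one.

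The loss may therefore be small. Planned power of 81% leaves little room for it, however, and a null Arm 2 result under the present wording would be harder to interpret.

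**What to change.** In the Analytic Plan and its Aim 1 paragraph:

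- Restrict adjustment in the Aim 1 BMI models to the stratification factors and variables fixed before the index WCV: EHR and census data, pre-visit telephone-survey items and demographics. For parent, household and child variables, these are the Covariate rows of Table 4.
- State that parent study-questionnaire scales labelled Mediator or Secondary Outcome do not enter the primary model, and report their balance by arm descriptively only.
- Reconcile the Source note with the Aim 1 text and row 11 on when each questionnaire was taken relative to the visit.

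Admitting a scale only for children whose questionnaire preceded the visit is less workable, because the covariate would then be usable for only some of the sample. The documents also do not say that completion dates are held for every questionnaire.

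The cost is a sentence or two in the analysis plan and a corrected table note. The sample size does not change and no new data are needed. The small downside is losing a few covariates that might have added precision.

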Sample Size and Power

Our preliminary data comparing the change in BMIz between WCV vs. **PRO WCV** yielded a difference of 0.05 units.⁶ This corresponded to an effect size (Cohen's d) of approximately 0.20 of a standard deviation. Additionally, based on our preliminary data and the literature, we estimate the intra-cluster correlation (ICC) to be 0.005 to account for the clustering of participant families within PCP. We recognize that participants may be lost to follow up during the course of the study or that we will not recruit equal number of participant families across all PCPs. Therefore, our sample size calculations further assume a coefficient of variation (COV) equal to 0.25 to account for this potential imbalance. This parameter being greater than 0 (i.e., equal sample size across clusters) increases the required sample size. Lastly, to account for two *a priori* statistical comparisons in Aim 1 (**WCV vs PRO WCV**, **WCV vs. PRO WCV + Food Care**), the significance level is set at 2.5%. **Table 2** reports the required sample size for enrollment under the stated assumptions. All calculations assume 80% power and an overall significance level of 5% such that each of the two comparisons will be made at the 2.5% significance level.

The software PASS v15 was used for all calculations, specifically the module for cluster randomized trials for two means. Table 2 reports the required sample size for enrollment under the above stated assumptions (reproduced in this response). We also varied the effect size to additionally include 0.25 and using 20 and 25 PCPs per arm to understand how varying-the

parameters affected the sample sizes. For example, assuming an effect size of 0.20, ICC of 0.005, COV of 0.25, 80% power, and 0.025 significance level, the study would be required to enroll 28 participant families per PCP per arm for a total of 560 families per arm. However, we further inflated the sample size to account for 7% of participants not receiving allocated treatment (i.e., WCV completed by a PCP in a different Arm than scheduled) and a 10% dropout at 1 year. This yields a sample size of 675 per arm or, with rounding, 33 families per each of 20 PCPs, for a total of 675 per arm (N=2,025 across all three arms).

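### Both primary contrasts are tested at a fixed 0.025; Holm's procedure would raise power within the same 5% family-wise bound (a cheap improvement, not an error)

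*Combined protocol and SAP*

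**What the plan says.** Sample Size and Power names two a priori comparisons, WCV vs PRO WCV and WCV vs PRO WCV + Food Care. It sets an overall level of 5% such that "each of the two comparisons will be made at the 2.5% significance level". Analytic Plan, Aim 1, repeats the rule for the mixed-model contrasts, which are written "to estimate the effect of the interventions compared to standard WCV using a two-sided alpha of 0.025 to account for multiple testing".

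The two sections agree. Together they describe an equal, fixed Bonferroni split, although that name is not used. No step-down, gatekeeping or other rule passes alpha from a rejected contrast to the remaining one. The sample size is built on the same 0.025 and promises 80% power for each comparison. It makes no claim about the power to show both interventions effective.

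**The concern.** Under a fixed split, a contrast with a p-value between 0.025 and 0.05 fails even when the other contrast has already been rejected at 0.025. Holm would reject it in that case and still hold the family-wise error at 5%.

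The case is not remote. The Aim 1 hypothesis is that change in BMIz is lower in both intervention arms, and Arm 3 contains the Arm 2 intervention plus Food Care. The Outcomes section also says that the findings should tell parents what to expect from each of the three options, so both comparisons matter. At stake is the chance of missing one effective intervention when both work.

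**Working it through.** **1. The plan's own figure.** Inputs from Sample Size and Power: "assuming an effect size of 0.20, ICC of 0.005, COV of 0.25, 80% power, and 0.025 significance level", with 20 PCPs per arm.

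- Without clustering: n = 2(z₀.₉₈₇₅ + z₀.₈₀)²/d² = 2(2.2414 + 0.8416)²/0.20² = 475.3, so 476 per arm.
- Design effect for unequal clusters of mean size m: (1 + (m−1)·ICC)/(1 − CV²·L(1−L)), where L = m·ICC/(m·ICC + 1 − ICC). At m = 28 it is 1.143.
- 475.3 × 1.143 = 543 per arm, or 27.2 per PCP, which rounds up to 28. At m = 27 power is 79.95%, just short of 80%. This matches the plan's "28 participant families per PCP per arm for a total of 560 families per arm".
- The plan then inflates to "account for 7% of participants not receiving allocated treatment" and "a 10% dropout at 1 year": 560/(1 − 0.07 − 0.10) = 674.7, so 675 per arm, as stated.

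Of the variants tried, only two-sided 0.025 with the normal approximation gives 28 and 560. Two-sided 0.05 gives 22 per PCP, and a t reference with cluster degrees of freedom gives 30. So the sample size does use the split alpha.

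**2. Holm's error bound.**

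- Both nulls true: a false rejection needs the smaller p-value to be at most 0.025, which has probability at most 2 × 0.025 = 0.05.
- One null true: a false rejection needs that contrast's p-value to be at most 0.05.

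Neither step uses the correlation between the contrasts.

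**3. Size of the gain.** With equal arms and a shared control, the two contrasts have correlation v/(2v) = 0.5, where v is the variance of one arm mean. Take each test at exactly 80% power at 0.025 (noncentrality 2.2414 + 0.8416 = 3.083), with both effects at 0.20.

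- Fixed split: 0.800 per comparison, 0.687 for both, and 0.800 + 0.800 − 0.687 = 0.913 for at least one.
- Holm adds, for each contrast, the probability that its p-value lies in (0.025, 0.05] while the other is at most 0.025. That is 0.0456.
- Holm per comparison: 0.800 + 0.0456 = 0.846.
- Holm for both: 0.687 + 2 × 0.0456 = 0.778.
- At least one: unchanged, because the first step is the same.

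| Scenario | Quantity | Fixed split | Holm |
|---|---|---|---|
| Both effects 0.20, exactly 80% power | per comparison | 80.0% | 84.6% |
| | both | 68.7% | 77.8% |
| | at least one | 91.3% | 91.3% |
| Both effects 0.20, 560 per arm | per comparison | 81.3% | 85.7% |
| | both | 70.5% | 79.3% |
| One effect 0.20, other null, exactly 80% power | effective arm | 80.0% | 80.2% |
| | null arm (false rejection) | 2.5% | 4.2% |
| One effect 0.20, other null, 560 per arm | effective arm | 81.3% | 81.5% |
| | null arm (false rejection) | 2.5% | 4.3% |
| Both null | family-wise error | 4.65% | 4.65% |

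**4. Intervals.** A 97.5% interval excludes zero only when p < 0.025. Every rejection that Holm adds has p between 0.025 and 0.05, so its 97.5% interval includes zero.

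**The case against.** The strongest case for leaving the plan alone has four parts.

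- **The plan is sound.** The split is valid and pre-specified, and the sample size follows from it. This stands. A reader might infer that multiplicity control is faulty or that the trial is underpowered by its own standard. The documents support neither: they promise 80% per comparison, the calculation delivers it, and they never promise power for both.
- **The change has a price.** A reader might infer that Holm costs nothing because the 5% bound is shared. The bound is shared, but the realised error is not. If one arm has no effect and the other works as planned, false rejection for the null arm rises from 2.5% to about 4.3%. The fixed split also pairs exactly with 97.5% intervals, which is a legitimate reason to prefer it. Both points stand.
- **The gain depends on both arms working.** The preliminary data cover only WCV vs PRO WCV, so an Arm 3 effect of 0.20 is an assumption. With one effective arm the gain is negligible. This stands too, although an effect in both arms is what the Aim 1 hypothesis states.
- **The change would come late.** The text records changes from September and October 2022 and one made just after 50% enrollment, and the data analyst and project manager are not blind. Relaxing a rejection threshold after treatment comparisons had been seen would not be acceptable. The documents do not show whether any have been seen, so timing is a condition of the fix.

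None of this alters the fact that Holm never rejects fewer hypotheses than the fixed split within the same 5% bound.

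**Conclusion.** This is an optional but worthwhile efficiency gain on a plan that is correct as written. If both interventions have the planned effect, Holm adds about 4.6 points of power per comparison (80.0% to 84.6%) and about 9 points for showing both (68.7% to 77.8%). The chance of missing at least one effective arm falls from about 31% to about 22%. Holm adds nothing to the power for at least one arm, and almost nothing if only one arm works.

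The sizes rest on the normal approximation that reproduces the plan's 560, a correlation of 0.5, and an Arm 3 effect of 0.20. The error bound and the ordering of the two procedures rest on none of these. The higher realised error when one null is true, and the mismatch with 97.5% intervals at the second step, are real costs and should be stated with the change.

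**What to change.** Before any unblinded treatment comparison is seen, add a dated amendment, or a dated statement in the statistical analysis plan, that:

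- tests the two primary p-values by Holm: the smaller at two-sided 0.025 and, only if it is rejected, the other at 0.05;
- judges significance by the Holm-adjusted p-value, and reports the 97.5% intervals as simultaneous Bonferroni intervals, noting that a second-step rejection with p between 0.025 and 0.05 has an interval that includes zero;
- records that the family-wise bound remains 5%, and that with one true null the false-rejection rate for that arm can rise from 2.5% to about 4.3%;
- says whether the rule covers only the two primary contrasts, since Aim 1 has the secondary outcomes follow the same strategy.

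The sample size and the stated 80% minimum power per comparison stay as they are, because the fixed split remains a lower bound on Holm's power. The cost is a short text change, with no change to the model or data collection. If unblinded comparisons have already been seen, the fixed split should stay.
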